### 7.2 DEPRESSION HISTORY QUESTIONS

The following patient questions used to assess depression will be optional at baseline and at each annual follow-up.

- Have you had any office visits in past year for treatment of depression? (Y/N)
  - If Yes: Approximately how many visits?
  - If Yes: Are you taking any medication for treatment of depression?
     If Yes: How many months have you taken the medication?

### 7.3 PATIENT QUESTIONNAIRES

Patient questionnaires to measure effectiveness will be optional at baseline and at all follow-ups. The following validated, patient-reported outcome questionnaires are *strongly recommended* for all patients at baseline and follow-up:

- IIEF-5/SHIM erectile function questionnaire
- EHS erection hardness questionnaire
- SF-12 health-related quality of life (HRQOL) questionnaire

The following validated, patient-reported outcome questionnaires are recommended for all patients with post-prostatectomy ED or incontinence:

- AUA-SI/IPSS urinary symptom questionnaires
- UCLA-PCI urinary, sexual and bowel function and bother questionnaire

The questions for each individual questionnaire are provided in the Appendix.

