Penile Measurements	0	0	0	0
Incontinence Data	0	0	0	0
Patient Questionnaires	SE	SE	SE	SE
Clinical Study Events/Complications	R†	R†	R†	R†

\* The same assessments, evaluations, questionnaires that were completed at baseline should be completed at follow-up

[figure not shown]
R = Required, O = Optional, SE = Strongly Encouraged, N/A = Not Applicable.

 $\dagger = if applicable$ 

- Demographics and Characteristics age, race/ethnicity, concomitant medical conditions and medications
- ED History primary etiology of ED, previous ED treatments (optional)
- Depression History query for any treatment of depression in past year optional at baseline and at annual follow-up
- Implantation Procedure Details surgical procedure details and implant model information, patient status post-op
- Device Use and Satisfaction query for device use and device satisfaction
- Penile Measurements pre-op flaccid and stretched length and girth, intra-op inflated penile length and girth and deflated stretched length, and post-operative inflated length and girth measurements, by physician
- Incontinence Data Daily pad use, pad weight tests, urodynamics, post-void residual (PVR) volume maximum flow rate

- Patient Questionnaires IIEF-5/SHIM erectile function questionnaire; EHS erection hardness question; SF-12 health-related quality of life questionnaire; AUA-SI symptom questionnaire; UCLA-PCI urinary, sexual and bowel function and bother questionnaire
- Clinical study events device or procedure related complications (adverse device effects/events), device malfunctions, revision procedures related to the device or implantation procedure

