### 7 DATA COLLECTION

Data will be collected via internet-based electronic data capture (EDC) with paper based questionnaires for collection of patient-reported outcomes (PRO) data. The PRO data will be entered into the registry database by the physician, physician staff or BSC staff. The EDC module will be developed and maintained by BSC.

Physicians are not required to complete all data fields in the database. Each will be asked to enter the required data at baseline/procedure and one-year follow-up for each

patient and optional data based on the information that they collect per their own standard of care.

Additional outcomes will be collected at whatever time frames are deemed appropriate by the physician, based on their standard of care for treatment of ED.

This is an observational collection of prospective patient data, with the following data required for each enrolled physician and patient:

- basic practice information for each physician
- baseline/pre-operative patient information: age, race/ethnicity, primary etiology of ED, relevant concomitant medical conditions and concomitant medications that might impact ED
- implantation surgery data: date of procedure, surgical approach, implant model type, drain, dressing, concurrent procedures, significant corporal fibrosis or scarring noted, curvature correction procedure(s) (e.g., for Peyronie's disease), and patient status post-op
- 1-year post-operative follow-up (at a minimum): each patient is asked 3 standardized questions during a visit or by phone to record any potential device related complications and their outcomes, patient satisfaction with implanted device(s) and use of device.

Refer to Table 1 for the study data collection schedule.

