#### Endpoint:

The endpoint is the change in IIEF-5 total scores from baseline to 1-year post-operative follow-up.

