#### Statistical Analysis:

The IIEF-5 total scores will be computed for each patient at baseline and 1-year follow up, and the change from baseline to 1-year follow up will be calculated. Descriptive summary statistics including mean, median, standard deviation (SD), and range will be generated by each device type and overall for all BSC penile prostheses recipients. For within patient change at 1-year follow up compared to baseline, signed rank sum test or paired t-test may be used when applicable.

Additional analyses may also be used to summarize the values at the other follow-up time points with data available along with changes from baseline for each device type and overall for all BSC penile prostheses recipients. Mixed effects model may be used to estimate the change from baseline across follow up visits when appropriate.

In addition, the number and percentage of patients with IIEF-5 scores meeting the following criteria will be calculated at baseline and at each post-treatment time point for each device type and overall:

- $\circ \leq 7$  points (severe ED)
- 8 to 11 points (moderate ED)
- 12 to16 points (mild-moderate ED)
- 17 to 21 points (mild ED)
- $\circ$  ≥ 22 points (no ED)

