#### Determination of Patients for Analysis:

All enrolled patients that received a BSC penile prosthesis with data available will be included.

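### For the five optional questionnaires, the only change analysis the plan commits to is a descriptive summary of men with both forms, and nothing examines who those men are

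*Combined protocol and SAP*

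**What the plan says.** **Status of the forms.** Section 7.3 states "Patient questionnaires to measure effectiveness will be optional at baseline and at all follow-ups". IIEF-5, EHS and SF-12 are strongly recommended for every man. AUA-SI and UCLA-PCI are recommended only for men with post-prostatectomy ED or incontinence. Table 1 in the synopsis uses the key "R = Required, O = Optional, SE = Strongly Encouraged, N/A = Not Applicable" and marks questionnaires SE in every column, never R. Its footnote adds "The same assessments, evaluations, questionnaires that were completed at baseline should be completed at follow-up". Section 7 says "Physicians are not required to complete all data fields in the database".

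**Endpoint and committed analysis.** Section 8.3.2 reads "The endpoint is the change in IIEF-5 total scores from baseline to 1-year post-operative follow-up", and Sections 8.3.3 to 8.3.6 use the same form for the other four instruments. Each section commits to a per-patient score difference ("the change from baseline to 1-year follow up will be calculated") summarised descriptively by device type and overall.

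**Discretionary analyses.** A signed rank or paired t-test is permitted where applicable. Each of the five sections also says "Mixed effects model may be used to estimate the change from baseline across follow up visits when appropriate". The synopsis adds GEE as an alternative. No model terms, covariance structure or condition for using the model are given.

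**Analysis set.** For every objective: "All enrolled patients that received a BSC penile prosthesis with data available will be included".

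We found no rule for missing questionnaires, no planned report of completion, no comparison of men with and without forms, and no sensitivity analysis.

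**The concern.** A change score exists only for a man who completed the form at both visits, and neither form is required. The required 1-year contact can be a telephone call with three standard questions (Section 7), while questionnaires are on paper. A man can therefore meet every 1-year requirement and supply no questionnaire.

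There are reasons to think completion may be related to outcome. The IIEF-5 items in Appendix 1 ask about erections and intercourse and offer no response for a man who is not sexually active. Section 7.3.2 ties the EHS to the most recent sexual encounter. Section 7.1 lists reasons for not using the device, including device problems, dissatisfaction and loss of a partner, and a man in that position may find the forms hard to answer.

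The registry's stated aim is real-world outcomes (Section 3.1), and Section 2.2 intends comparison with historical data. A mean change in an undescribed subset serves neither aim well, and the plan gives the reader no means of judging how far that subset represents all implanted men.

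**Working it through.** The documents give no completion rate, standard deviation or expected change, so there is no planned figure to reproduce. Only N (about 500 to 1500, Sections 5 and 8.1) comes from the documents. Every other input below is an assumption.

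**1. How many men have paired forms.** Let b and f be the completion rates at baseline and 1 year. If completion is independent between visits, the paired share is b × f and the share with at least one form is 1 − (1 − b)(1 − f). Whatever the dependence, the paired share lies between max(0, b + f − 1) and min(b, f).

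| b = f | Paired share, independent | Bounds | Paired men, N = 500 / 1500 | At least one form | Of those, not in the change score |
|---|---|---|---|---|---|
| 50% | 25% | 0–50% | 125 / 375 | 75% | 50/75 = 67% |
| 70% | 49% | 40–70% | 245 / 735 | 91% | 42/91 = 46% |
| 90% | 81% | 80–90% | 405 / 1215 | 99% | 18/99 = 18% |

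Dependence matters. At 70% per visit, if the same men complete both forms, 70% are paired and nobody has only one of the two.

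**2. Bias of the paired mean.** Bias = (1 − paired share) × (mean change in men with both forms − mean change in the rest). For an assumed 2-point gap:
- 25% paired: 0.75 × 2 = 1.50 points
- 49% paired: 0.51 × 2 = 1.02 points
- 81% paired: 0.19 × 2 = 0.38 points

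The bias takes the sign of the gap, which is unknown.

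**3. Precision gained by using men with one form.** Assume two visits, equal variances, correlation r, b = f, independent completion, and forms missing completely at random. The variance of the mean change from the mixed model, relative to the paired mean, is 1 / [1 + (1 − r)(1 − f)/f]. For r = 0.2 to 0.8:
- f = 50%: 0.56 to 0.83
- f = 70%: 0.75 to 0.92
- f = 90%: 0.92 to 0.98

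**4. What a mixed model does about selection.** We simulated 400,000 men, all with a baseline form. Assumed IIEF-5 means were 8 then 20, SDs 4 and 5, correlation 0.3. About 67% to 69% completed the 1-year form, with higher scorers set to complete more often. The two values in each cell are for weaker and stronger selection.

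| 1-year completion depends on | Bias, paired mean | Bias, maximum likelihood using all men |
|---|---|---|
| Baseline score | −0.35, −0.68 | 0.01, 0.02 |
| 1-year score itself | +0.57, +1.06 | +0.68, +1.29 |

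The model removes bias when selection works through a score that was observed. It does not when selection works through the missing score, where it was slightly worse than the paired mean.

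**The case against.** The plan is less restrictive than it may look. A reader might infer that it analyses only men with both forms and throws the rest away. The text does not support that. A mixed model is named in each of the five questionnaire sections, GEE is named in the synopsis, and the IIEF-5, EHS and AUA-SI category counts at each time point need no pairing. The paired test is no more firmly planned than the model, since both are optional. Table 1 also asks that forms used at baseline be repeated, which should raise the paired share.

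A reader might also infer that the results will look too good because unhappy or explanted men do not return. No passage says so. Section 7.4 has patients told to discuss device problems with their physician, and Section 4 allows follow-up by telephone or mail, so men with problems could be seen more often.

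Finally, this is a descriptive registry with no alpha, power or confirmatory questionnaire test. Post-operative success is judged by device use and, in the synopsis, satisfaction, both of which are required at 1 year.

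These arguments limit the point but do not remove it. Permitting an unspecified model does not commit anyone to fitting it, the pairing instruction does nothing for a man with no baseline form, and the absence of any completion report or comparison is unanswered. A descriptive registry depends especially on showing whom its summaries describe.

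**Conclusion.** The point holds in limited form. For Objectives 2 to 6 the committed change analysis is a descriptive summary of men with both forms. The alternatives are named but discretionary and unspecified, and selection is left unexamined.

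The size and direction of any bias cannot be found from the documents. The 25% to 81% paired share and the bias of about 0.4 to 1.5 points rest on assumed completion of 50% to 90% per visit, independence between visits and an assumed 2-point gap. They show scale only and are not estimates for this registry.

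It would also be too strong to say that a mixed model cures the problem. It improves precision and handles selection on observed scores, but not selection on the 1-year score itself, and it recovers nothing for a man with no form at any visit. That is why the completion report, the comparison and a sensitivity analysis are needed beside it. This is a cheap improvement that should be made.

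**What to change.** 1. **Main analysis.** In Sections 8.3.2 to 8.3.6, make a longitudinal mixed model the main analysis of 1-year change. Treat baseline as one of the repeated outcomes so that men with only one form contribute. Enter visit as a factor, with age, etiology, implant type and site as covariates. State the covariance structure and whether covariate-by-visit terms are included. Keep the paired summary as supportive.
2. **Post-implant information.** Do not enter 1-year device use, satisfaction or explant status as ordinary covariates, because that conditions on consequences of the implant and changes the quantity estimated. Use them as auxiliary variables in multiple imputation or weighting.
3. **Sensitivity analysis.** Add a simple check for completion that depends on the 1-year score, such as shifting imputed 1-year scores by a range of fixed amounts in both directions. Each point of shift moves the mean change by the share of men whose 1-year score is imputed (for example 0.3 points if 30% are imputed).
4. **Completion and comparison.** Report completion by visit, site and device. For men with and without paired forms, tabulate baseline characteristics and the required 1-year use, satisfaction and complications. Do this within each form's target group: all implanted men for IIEF-5, EHS and SF-12, but only men with post-prostatectomy ED or incontinence for AUA-SI and UCLA-PCI. Otherwise a man never meant to receive a form is counted as missing.

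**Cost.** SAP wording, one or two tables and a little more analysis. The comparison uses data the registry already requires, so no new collection is needed. The downside is that model assumptions must be stated, including how the 0 to 4 EHS is treated.

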### 7.3.1 International Index of Erectile Function-5 / Sexual Health Inventory for Men (IIEF-5/SHIM)

The IIEF-5 (also known as the SHIM) is a validated, self-report questionnaire with a 25point maximum score, summed from responses to four questions derived from the erectile function domain (items 2, 4, 5, and 15) and one question from the intercourse satisfaction domain (item 7) of the broader validated 15-item IIEF questionnaire used to assess sexual function in multiple domains. Severity of ED is categorized based on the following IIEF-5 domain scores established and validated in previous studies:

Severe—5 to 7 Moderate—8 to 11 Mild-Moderate—12 to16 Mild—17 to 21 No ED—22 to 25

# 7.3.2 EHS Erection Hardness Questionnaire

Patients will be asked to respond to the Erection Hardness Score (EHS) questionnaire once per year or at each follow-up visit to assess erection hardness based on their most recent sexual encounter(s). The EHS has a range of responses from 0 to 4 with higher scores corresponding to a more firm or rigid erection.

# 7.3.3 SF-12 Health-related Quality of Life (HRQOL) Questionnaire

The SF-12v.2 Health Survey is a generic measure and does not target a specific age or disease group. It is a shorter version of the SF-36V2 Health Survey that uses 12 questions to measure function health and well-being from the patient's point of view. The SF-12 quantifies HRQOL into two composite scores, the Physical Component Summary (PCS) and Mental Component Summary (MCS) scales. This survey also quantifies HRQOL into the same eight multi-item subscale domains used in the SF-36 with one or two questions in each domain: physical functioning, emotional well-being, general health, pain, energy, social functioning, and role limitations (problems with work or other daily activities) as a result of physical or emotional health. Each individual domain and the component summary scores (PCS and MCS) are calculated and converted to a standardized 0-100 scale, with higher scores indicating better HRQOL.

# 7.3.4 American Urological Association – Symptom Index (AUA-SI)

THE AUA-SI (comprised of 7 of the 8 questions of the International Prostate Symptom Score, or IPSS) is used to quantify urinary irritative/obstructive symptom frequency and severity and is scored on a scale of 0–35 based on the summary of the values for each item, with higher scores corresponding to worse outcomes. Classification of urinary irritative/obstructive symptoms based on these scores are as follows:

Mild – 0 to 7

Moderate – 8 to 19 Severe – 20 to 35

# 7.3.5 UCLA-Prostate Cancer Index (UCLA-PCI) Questionnaire

The UCLA-PCI assesses disease-specific, organ targeted health related quality of life (HRQOL) in six scales or domains that are of special concern to men treated for prostate cancer. Each UCLA PCI domain is scored on a scale of 0–100 points with higher values representing better outcomes.

### 7.4 SAFETY ASSESSMENTS

Prior to enrollment in the study, patients should be informed by the physician of all known potential risks and discomforts that may be associated with the implantation of a BSC penile prosthesis, or with the study evaluations and data collection. The implantation of a BSC penile prosthesis is a standard medical treatment for ED, and no experimental interventions, tests or procedures are included in this observational Registry study. A complete list of potential adverse device effects and surgery or device related complications that may occur during or after the implantation of the BSC devices can be found in the device specific IFU and/or OR and Patient Manuals.

As per the OR Manual for the penile prosthesis, after penile prosthesis implantation, the Principal Physician is responsible for checking with the patient for any signs of complications, and for reporting device complications in compliance with local regulations (e.g. IRB/EC, country) for a market-released device. The physician should continue to have contact with the patient at least on an annual basis to ask if he has noticed any changes in device functioning (e.g., cylinders losing rigidity), and to check for signs of complications such as infection or erosion. Patients should be instructed to discuss any changes noticed in the function of their prosthesis or problems that may develop after implantation surgery with their physician.

# 7.4.1 CLINICAL STUDY EVENTS

Clinical study events to be collected for assessment of safety include complications (adverse device effects/events), device malfunctions, and revision procedures related to the device or implantation procedure. At follow-up, including the required 1-year post-operative visit or telephone call, the following standardized, non-validated question will be used to determine whether any complications with the device have occurred:

• Have you had any surgery on your penis or problems with the device since your penile prosthesis was implanted? (Y/N)

A clinical study event data form will be provided to record any events that occur during or after surgical implantation of a BSC penile prosthesis device. Any reported intraoperative or post-operative device or surgery related complications should be recorded at the time of procedure and any follow-up visits (for BSC products only). The information recorded will include the following:

- Complication
- Treatment
- Location of treatment
- Resolution (Resolved or Continuing)

BSC personnel will follow up with the physician to obtain additional available details, if needed, related to any reported complication that results in a serious adverse device effect, or device deficiency that could have led to a serious adverse device effect, or is severe and may pose unreasonable risk, or potential for death, or serious injury to the patient.

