    - Total number of RTEs per cylinder (0, 1, 2, 3, 4)
    - Total length of RTEs per cylinder (specify: 0.5 to 6.5 cm)
  - AMS 700® Penile Prosthesis (3–piece inflatable)
    - InhibiZone®-impregnated (Y/N)
    - Cylinder type (CX, LGX, CXR, Ultrex, CXM)
    - Cylinder length (10, 12, 14, 15, 16, 18, 21, 24 cm)
    - Total number of RTEs per cylinder (0, 1, 2, 3, 4)
    - Total length of RTEs per cylinder (specify: 0.5 to 7.5 cm)
    - Pump type (MS Pump, Tactile pump, Inflate/Deflate)
    - Preconnect (Y/N)
    - Reservoir (Spherical 65 ml, Spherical 100 ml, Conceal 100 ml)
    - Reservoir placement (space of Retzius, Sub-muscular, Sub-Scarpa's fascia, other – specify)
    - Reservoir separate incision (Y/N)
- Drain (Y/N)
  - o If Yes, Type
- Dressing
  - None, compression/mummy wrap, noncompressive dressing
- Concurrent procedures (Y/N)
  - If Yes, specify procedure(s): ventral

phalloplasty, ligament release, circumcision, suprapubic fat pad reduction, spermatic cord/testicular procedure, AMS 800 (single or multiple incision), sling (specify sling type and single or multiple incision), other - specify

- Significant corporal fibrosis or scarring noted (Y/N)
- Curvature correction procedure(s) (e.g., for Peyronie's Disease)(Y/N)
  - If Yes: Initial intraoperative curvature measurement (angle of curvature with inflated device using a goniometer or protractor)
  - If Yes: Correction technique (Wilson/Delk remodeling, tunical incision, incision and grafting, or plication)
  - Curvature measurement after correction
  - Second correction? If Yes, same set of questions as above.
- Patient status post-op: Admitted/inpatient/≥24 hours or same day discharge/outpatient/<24 hours
  - If admitted/inpatient/≥24 hours is chosen, include: number of days in the hospital
- Length of procedure (measured from time of first incision to time of closure)
- Intra-operative penile length measurement with device inflated (measured from suprapubic fat pad to tip)
- Intra-op penile girth measurement with device inflated (circumference measured 1cm proximal to the proximal end of the corona)
- Intra-op stretched penile length measurement with device deflated (measured from suprapubic fat pad to tip)
- Foley in place at discharge? (Y/N)

Follow-up is required 1 year post-operatively. *Additional follow-ups will be determined per the physician's standard practice up to 5 years.* Follow-up data will include:

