- Query for any device related complications and their outcomes by asking patients if they have had any surgery on their penis or problems with the device since their penile prosthesis was implanted (Y/N)
- Patients will be asked:
  - How satisfied they are with the device(s) (using a 5-point scale)

- If they are using the device (Y/N)
  - If yes, how often they are using the device (less than once per month or more than once per month)
     *o* How many times per month?
  - If no, why aren't you using the device (loss of partner, partner disinterest, device problem, device dissatisfaction, health decline, other – describe, other device use reason).
  - If yes, and not using the device as often as desired, or if dissatisfied with the device, indicate why ((loss of partner, partner disinterest, device problem, device dissatisfaction, health decline, other – describe, other device use reason).
- Number of pads used daily (if incontinence indicated pre-operatively)
- Pad weight (24-hour test) (if incontinence indicated pre-operatively)
- Penile length measurement with device fully inflated (measured from suprapubic fat pad to tip)
- Penile girth measurement with device fully inflated (circumference measured 1cm proximal to the proximal end of the corona)
- Stretched penile length measurement with device deflated (measured from suprapubic fat pad to tip)
- Patient query any office visits in past year for treatment of depression Y/N
  - o If Yes: approximately how many visits
  - If Yes: taking any depression medication
- Effectiveness/quality of life assessments

Patient questionnaires to measure effectiveness will be optional at baseline and at all follow-up visits. Included are the following validated, patient-reported outcome questionnaires:

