### 4 REGISTRY DESIGN SUMMARY

The PROPPER Registry is a post-market, multi-center, non-interventional, observational collection of clinical outcomes for patients implanted with a BSC penile prosthesis for the treatment of erectile dysfunction.

As an observational collection, the registry does not dictate patient selection for implantation of BSC devices, and does not direct physicians in the medical and surgical management of patients. Physicians are free to select and manage their patients according to their usual practice. Concomitant urological procedures are allowed and will be recorded. However, outcomes data on these procedures will not be collected, with the exception of select data for any concomitantly implanted AMS 800 Artificial Urinary Sphincters or AdVance slings for the treatment of incontinence.

BSC recommends that all devices are implanted according to the device specific Instruction for Use (IFU) and/or Operating Room (OR) manuals and the site or physician's standard of care.

Patient data will be collected from the baseline/pre-operative visit, the procedure, and follow up evaluations which will occur according to each physician's standard of care, up to 5 years post-operatively. A 1=year follow up evaluation will be required, and a 2-year follow-up evaluation will be strongly encouraged. Follow-up evaluations may occur during visits with the physician and/or by telephone or mail.

Each physician will determine if the device implantation procedure was successful based on his/her standard of care. Any reported intra-operative complications will be collected in the registry database. Success will be measured post-operatively by querying patients about device use.

The PROPPER Registry is designed to obtain post market safety and effectiveness information as well as to serve as an active surveillance system for collecting device related events or complications and malfunctions in patients implanted with BSC penile prostheses and reporting product complaints to BSC. This will provide a robust database of clinical information from which a number of analyses can be performed.

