#### Endpoint:

- Complications (adverse device effects/events)
  - Intra-operative device or surgery related complications reported during Implantation visit (e.g., cylinder crossover)

- Post-operative device or surgery related complications reported during follow-up (e.g., mechanical malfunction, infection)
- Unanticipated and serious adverse device effects (per ISO 14155:2011)
- Deaths (related to the device or implantation procedure)
- Device Malfunctions
  - Device deficiencies or malfunctions (per ISO 14155:2011)
- Revision procedures related to the device or implantation procedure

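### The one scripted complication question is narrower than the safety endpoint, so surgery-related complications may be under-ascertained in men followed only by telephone

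*Combined protocol and SAP*

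**What the plan says.** Section 7.4.1 gives a single standardized, non-validated question for complications at follow-up: "Have you had any surgery on your penis or problems with the device since your penile prosthesis was implanted? (Y/N". The sentence introducing it says that this "question will be used to determine whether any complications with the device have occurred". The synopsis gives it the same scope in its follow-up list: "Query for any device related complications and their outcomes by asking patients if they have had any surgery on their penis or problems". Section 7 says that at the 1-year contact "each patient is asked 3 standardized questions during a visit or by phone to record any potential device related complications and their outcomes"; the other two questions concern satisfaction and use.

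The endpoint in section 8.2 is wider. Its post-operative component is "Post-operative device or surgery related complications reported during follow-up (e.g., mechanical malfunction, infection". Revision procedures and device malfunctions are further components. The analysis is a count of events and a proportion of patients by complication category, by device type and overall, plus a Kaplan-Meier 1-year rate for major complications.

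The synopsis and section 4 require only the 1-year evaluation, strongly encourage one at 2 years, and leave the rest to each physician's standard of care. On mode, section 4 says "Follow-up evaluations may occur during visits with the physician and/or by telephone or mail". Sections 5.1, 7 and 7.4.1 name only a visit or the telephone for the 1-year questions.

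There are other routes into the database. Section 7.4.1 provides a clinical study event form for reported complications of the device or the surgery, and Table 1 marks these events as required, if applicable, at every contact. Section 7.4 makes the physician responsible for checking with the patient for signs of complications, and asks that patients be told to raise post-operative problems with their physician.

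**The concern.** Safety is the first-listed objective, and section 4 describes the registry as active surveillance. For a man whose only study contact after discharge is the 1-year call, the question in section 7.4.1 is the only scripted safety prompt. It has two limbs: an operation on the penis, and a problem with the device. A complication of the operation that led to neither falls outside it, although the endpoint counts it.

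The error would run one way, towards under-counting. It could also vary with how the man was contacted. Neither the synopsis list of follow-up data nor Table 1 includes contact mode, so on the documents the analysis could not describe that variation.

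**Working it through.** The documents state no complication rate, so there is no planned figure to reproduce. The check is a comparison of texts, followed by an illustration of scale.

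**Step 1: scope of question against scope of endpoint.**

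- Revision through the penis: in the endpoint, and caught by the first limb.
- Mechanical malfunction: in the endpoint, and caught by the second limb.
- Wound infection treated without an operation, device working: in the endpoint (infection is its own example), but caught only if the man regards it as a device problem.
- Bleeding or wound problem managed without re-operation: the same.
- Persistent pain attributed to the operation: the same.
- Operation at a reservoir incision away from the penis (the synopsis collects "Reservoir separate incision (Y/N"): not literally surgery on the penis, but the reservoir is an AMS 700 component, so the second limb may well catch it. This is a weak example.

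The residual is therefore surgery-related complications with neither penile surgery nor a perceived device problem. The stated purpose of the question is limited to the device in sections 7.4.1 and 7 and in the synopsis, so this is not one loose phrase.

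**Step 2: do the other routes cover the residual?**

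- Event form (section 7.4.1, Table 1): right scope, but it records what has been reported and does not prompt for it. Section 7.4.1 ties recording to the procedure and follow-up visits.
- Physician check and patient instruction (section 7.4): can be done verbally, so they can work by telephone, but no wording is given. The specific question described there concerns device functioning. Physical signs cannot be examined by telephone.
- Reports of serious or unanticipated device effects and deaths (section 16.1): start once the physician learns of the event, so they depend on ascertainment.

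These routes reduce the gap without closing it.

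**Step 3: scale, with assumed inputs.** Suppose all other complications are fully captured. Let f be the share of complications in the residual group, m the share of those men reached only by telephone or mail, and s the chance that the event is captured anyway. Then:

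relative under-count = f × m × (1 − s)

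None of the three inputs is in the documents. The assumed ranges are f = 10% to 40%, m = 25% to 75%, s = 0% to 80%.

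- Low: 0.10 × 0.25 × (1 − 0.80) = 0.005, or 0.5%.
- Middle: 0.20 × 0.50 × (1 − 0.50) = 0.05, or 5%.
- High: 0.40 × 0.75 × (1 − 0) = 0.30, or 30%.
- If the other routes capture everything, s = 100% and the loss is 0.

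These are fractions of the true number of complications, not percentage points of patients.

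**The case against.** The strongest case on the other side is that the question does not stand alone. A complication known to the implanting practice reaches the database through the event form whatever the man answers at 1 year. The form also records where treatment took place, so care elsewhere can be entered. The physician's check can be verbal, patients are told to raise problems, and a caller can probe an answer. The first limb should catch most re-operations. The endpoint is defined on reported complications, and a short prompt is a reasonable low-burden choice in a non-interventional registry.

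Most of this stands, and it limits the point to possible under-ascertainment. What remains is that every other route waits for the event to be noticed or volunteered, and none asks about complications of the operation in standard words.

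A reader might infer more than the documents support:

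- That events will certainly be lost, or a stated number of percentage points. No document gives a rate, a telephone share or a capture probability.
- That the Kaplan-Meier rate is materially biased. It is limited to major complications, a term left undefined, and nothing shows that an infection treated without surgery would count.
- That mail is an equal weakness for the required contact. It appears only in the general sentence in section 4.
- That comparisons between sites will mislead. Section 8 plans no comparison of complications by site or contact mode.

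**Conclusion.** The point holds as a scope mismatch with a possible, one-directional effect. The only standardized complication question is narrower than the endpoint it serves. Surgery-related complications that led to neither penile surgery nor a perceived device problem may be under-ascertained, mainly in men whose only required contact is the 1-year call. The exposure is chiefly in the descriptive counts and proportions by complication category, and less in the Kaplan-Meier rate.

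The size is not determinable from the documents. The illustrative range is wide because it rests wholly on assumed inputs, and it includes no loss at all. The recommendation rests on the wording gap and the low cost of closing it, not on any figure in that range.

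**What to change.** 1. Widen the question in section 7.4.1 and the matching synopsis item to cover the section 8.2 endpoint. For example: since the implant, have you had any problem with the device, or any infection, wound problem, pain, further operation or other treatment connected with the implant or the operation?
2. Change 'device related' to 'device or surgery related' where section 7 and the synopsis describe the purpose of the question, and align the introductory sentence in section 7.4.1.
3. Record the mode of each follow-up contact (visit, telephone, mail) and describe complication proportions by mode.

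This changes no treatment, visit or sample size. The cost is one reworded item, one added field, a few more unrelated reports for physicians to classify, and possibly slightly higher reported rates. If men have already been followed with the present question, show results before and after the change separately.
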